- Previously influenza vaccinated and unvaccinated subjects 36 months to < 5 years of age (Group 1) will be randomized to receive either QIV-HD at 30 µg HA/strain/dose or the unadjuvanted QIV-SD. Based on the early safety data review, the study will either stop (Group 1 does not pass safety review) or continue into Stage 2 .
- Previously influenza vaccinated and unvaccinated subjects 5 to 8 years of age (Group 9), will be randomized to receive either QIV-HD at 30 µg HA/strain/dose or the unadjuvanted QIV-SD. Based on the early safety data review, the enrollment of this age group will either stop (Group 9 does not pass safety review) or continue into Stage 2.
- Previously influenza vaccinated and unvaccinated subjects 9 to 17 years of age (hereafter will be referred to as subjects 9 to 17 years of age) will be divided into 2 groups (Group 12 and Group 13). Group 12 will be enrolled first and will be randomized to receive either QIV-HD at 30 µg, or 45 µg HA/strain/dose or the unadjuvanted QIV-SD. Once the enrollment of Group 12 is complete, subjects in Group 13 will be randomized to receive either QIV-HD at 60 µg or the unadjuvanted QIV-SD. Subjects 9 to 17 years of age will not undergo an ESDR.

Stage 2 will include 3 age groups (6 to < 36 months, 36 months to < 5 years, and 5 to 8 years) and will be conducted in the US:

- Previously influenza vaccinated and unvaccinated subjects 36 months to < 5 years of age (Group 2) will receive either QIV-HD at 45 µg HA/strain/dose or the unadjuvanted QIV-SD and previously influenza vaccinated and unvaccinated subjects 6 to < 36 months of age (Group 3) will receive either QIV-HD at 30 µg HA/strain/dose or the unadjuvanted QIV-SD. Based on the early safety data review, the study will either stop (Group 3 does not pass safety review), continue and skip to Stage 4 (Group 2 does not pass safety review), or continue to Stage 3 (Group 2 and Group 3 both pass the safety review).
- Previously influenza vaccinated and unvaccinated subjects 5 to 8 years of age (Group 10), will be randomized to receive either QIV-HD at 45 µg HA/strain/dose or the unadjuvanted QIV-SD. Based on the early safety data review, the enrollment of this age group will either stop (Group 10 does not pass safety review) or continue into Stage 3.

Stage 3 will include 3 age groups (6 to < 36 months, 36 months to < 5 years, and 5 to 8 years) and will be conducted in the US:

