Definition	Pain either present spontaneously or when the injection site is touched or injected limb is mobilized	Presence of a redness including the approximate point of needle entry	Swelling at or near the injection site  Swelling or edema is caused by a fluid infiltration in tissue or cavity and, depending on the space available for the fluid to disperse, swelling may be either soft (typically) or firm (less typical) to touch and thus can be best described by looking at the size of the swelling	Hardening at or near the injection site.  Hardening is caused by a slow diffusion of the product in the tissue leading to a thick or hard area to touch at or near the injection site and thus can be best described by looking at the size of the hardening.	Bruising is the result of the diffusion of blood in the skin from ruptured blood vessels that forms a purple or black and blue spot on the skin. It can be best described by looking at its size.

Intensity scale*	Grade 1: A type of adverse event that is usually transient and may require only minimal treatment or therapeutic intervention. The event does not generally interfere with usual activities of daily living.  Grade 2: A type of adverse event that is usually alleviated with additional therapeutic intervention. The event interferes with usual activities of daily living, causing discomfort but poses no significant or permanent risk of harm to the research participant.  Grade 3: A type of adverse event that interrupts usual activities of daily living, or significantly affects clinical status, or may require intensive therapeutic intervention.	Grade 1: $\geq 25$ to $\leq 50$ mm  Grade 2: $\geq 51$ to $\leq 100$ mm  Grade 3: $> 100$ mm	Grade 1: $\geq 25$ to $\leq 50$ mm  Grade 2: $\geq 51$ to $\leq 100$ mm  Grade 3: $> 100$ mm	Grade 1: $\geq 25$ to $\leq 50$ mm  Grade 2: $\geq 51$ to $\leq 100$ mm  Grade 3: $> 100$ mm	Grade 1: $\geq 25$ to $\leq 50$ mm  Grade 2: $\geq 51$ to $\leq 100$ mm  Grade 3: $> 100$ mm
-------------------------	---	--	--	--	--

\* For the subjective reaction of pain, subjects / parents / guardians will record the intensity level (Grade 1, 2, or 3) in the diary card. For the measurable reactions of redness, swelling, hardening, and bruising they will record just the size of the reaction, and the classification as Grade 1, 2, or 3 will be assigned at the time of the statistical analysis

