4.4 Derived Endpoints: Calculation Methods

4.4.1 Safety

4.4.1.1 Solicited Reactions

4.4.1.1.1 Daily Intensity

All daily records for solicited reactions will be derived into daily intensity according to the following classification: None, Grade 1, Grade 2, Grade 3, or Missing.

For measurable injection site reactions (Erythema/Swelling/Induration/Bruising):

- For subjects 6 months to 11 years of age

Grade 1: > 0 to < 25 mm

Grade 2: ≥ 25 to < 50 mm

Grade 3: ≥ 50 mm

- For subjects 12 to 17 years of age

Grade 1: ≥ 25 to ≤ 50 mm

Grade 2: ≥ 51 to ≤ 100 mm

Grade 3: > 100 mm

For measurable systemic reactions (Fever):

- For subjects 6 months to < 36 months of age

Grade 1: $\geq 38.0^{\circ}\text{C}$ to $\leq 38.5^{\circ}\text{C}$, or $\geq 100.4^{\circ}\text{F}$ to $\leq 101.3^{\circ}\text{F}$

Grade 2: $> 38.5^{\circ}\text{C}$ to $\leq 39.5^{\circ}\text{C}$, or $> 101.3^{\circ}\text{F}$ to $\leq 103.1^{\circ}\text{F}$

Grade 3: $> 39.5^{\circ}\text{C}$, or $> 103.1^{\circ}\text{F}$

- For subjects 3 to 17 years of age

Grade 1: $\geq 38.0^{\circ}\text{C}$ to $\leq 38.4^{\circ}\text{C}$, or $\geq 100.4^{\circ}\text{F}$ to $\leq 101.1^{\circ}\text{F}$

Grade 2: $\geq 38.5^{\circ}\text{C}$ to $\leq 38.9^{\circ}\text{C}$, or $\geq 101.2^{\circ}\text{F}$ to $\leq 102.0^{\circ}\text{F}$

Grade 3: $\geq 39.0^{\circ}\text{C}$, or $\geq 102.1^{\circ}\text{F}$

For the derivation of daily intensities the following sequential steps will be applied:

Solicited reactions (except Fever/Pyrexia) with an investigator occurrence recorded as “No” and with all daily records missing then all daily intensities will be derived as “None”.

For non-measurable solicited reactions, daily intensities will correspond to daily records reported in the clinical database. For measurable solicited reactions the daily measurements reported in the clinical database will be converted based upon the intensity scales defined in the protocol; this assumes a reaction that is too large to measure (non-measurable, “NM”) is Grade 3. Note the intensity could be considered “None” (not a reaction) in the analysis despite being considered a reaction by the investigator (eg, swelling measurement > 0 mm but < 25 mm in 12 to 17 years of age).

Note: The maximum intensity on the ongoing period is derived from the record of the maximum intensity/measurement after the end of the solicited period following the rule described above.

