5.1.1.2 Statistical Methods

For the cohorts controlled by the non-adjuvanted QIV-SD, results will be described per stage, according to vaccine received, per age group. Age groups will also be pooled within the same vaccine group for the main endpoints. When age groups are pooled, since age distributions between QIV-HD groups and the pooled QIV-SD group are different, the Simpson Paradox might exist. Therefore, each QIV-HD group (30 μ g, 45 μ g, and 60 μ g) will be compared with its corresponding and restricted QIV-SD group (ie, QIV-SD control group restricted to relevant study groups for comparison to QIV-HD at 30 μ g, QIV-HD at 45 μ g, and QIV-HD at 60 μ g respectively) to reduce the potential bias. If any of the stages are not completed, analyses for the higher dose or next stage will not be performed.

For the cohort controlled by the adjuvanted TIV, results will be described according to vaccine received.

For main safety analyses, results will be described based on both “after any vaccination” and “after each vaccination”.

For main immunogenicity analyses, results will be described based on both “after last vaccination” and “after each vaccination”. Subgroup immunogenicity analyses per previous vaccination status and/or baseline serostatus may be presented when appropriate. Comparison between each QIV-HD group (30 μ g, 45 μ g, and 60 μ g) and the pooled QIV-SD group will also be performed stratified on age groups for immunogenicity endpoints.

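### For the four measured injection-site reactions, the 9-to-17-year and age-pooled rates blend two size definitions; add a 9-11/12-17 split and common-threshold rows

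*SAP*

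**What the plan says.** SAP 4.4.1.1.1 sets out two millimetre scales under "For measurable injection site reactions (Erythema/Swelling/Induration/Bruising". From 6 months to 11 years the lowest grade is "Grade 1: > 0 to < 25 mm"; from 12 to 17 years it is "Grade 1: ≥ 25 to ≤ 50 mm". Grade 3 is 50 mm or more on the first scale and more than 100 mm on the second. Protocol Tables 9.1 to 9.3 agree. The SAP states the consequence openly: something the investigator regarded as a reaction may be analysed as none, the example being a "swelling measurement > 0 mm but < 25 mm in 12 to 17 years of age". SAP 4.4.1.1.3 then turns none into no occurrence.

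Pain has no size threshold. Protocol Table 9.3: "For the subjective reaction of pain, subjects / parents / guardians will record the intensity level (Grade 1, 2, or 3) in the diary card". For the measured reactions, the same footnote says of diary users that "they will record just the size of the reaction, and the classification as Grade 1, 2, or 3 will be assigned at the time" of analysis.

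Ages 9 to 17 form one reporting age group (Groups 12 and 13, SAP Table 3.1). SAP 5.1.1.2 describes results by age group and adds: "Age groups will also be pooled within the same vaccine group for the main endpoints". It compares each dosage with QIV-SD recipients from the same study groups, and plans an age-stratified comparison for immunogenicity only. Protocol 6.5 stratifies randomisation by previous influenza vaccination status and country. In Protocol 5.1.1, "Group 12 will be enrolled first" (30 µg, 45 µg and QIV-SD); Group 13 (60 µg and QIV-SD) follows.

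Fever counts from 38.0 °C at every age, but Grade 3 is above 39.5 °C under 36 months and 39.0 °C or more from 3 years.

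**The concern.** The age-12 cut changes whether a reaction is counted at all, as well as its grade. A 20 mm swelling is an occurrence at 11 years and none at 12; a 60 mm swelling is Grade 3 at 11 and Grade 2 at 12. Because the cut lies inside a reporting group, the 9-to-17 row is a weighted average of two different quantities, with weights set by whoever happens to enrol. Any composite that includes these four reactions inherits the blend, and so do tables pooled over age.

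The study aims to describe the safety of each dosage and to choose one for Phase III (Protocol 1.4 and 2). A reader using the 9-to-17 row as a reactogenicity rate, or setting it beside the 5-to-8-year row or another trial, would be comparing different definitions. The 30 and 45 µg arms are also not randomised concurrently with the 60 µg arm at these ages, so a difference in age mix between Groups 12 and 13 would appear as a dosage difference.

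**Working it through.** **Inputs from the documents.** The group sizes reproduce the planned total: 6×40 + 90 + 60 + 2×60 + 2×60 + 70 = 700. Planned QIV-HD pools, assuming Groups 6 and 7 receive 60 µg:

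| Dosage | Groups | Aged 9-17 | Matched QIV-SD aged 9-17 |
|---|---|---|---|
| 30 µg | 1, 3, 9, 12 | 30/120 = 25% | 10/40 = 25% |
| 45 µg | 2, 5, 10, 12 | 30/120 = 25% | 10/40 = 25% |
| 60 µg | 4, 6, 7, 11, 13 | 30/165 = 18.2% | 30/165 = 18.2% |

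**Assumptions.** The documents give no reaction rates and no 9-11 share. Let *a* be the rate of any reaction above 0 mm, *b* the rate of 25 mm or more, both the same at all ages, and *s* the share of the 9-to-17 group aged 9-11.

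**Step 1: the 9-to-17 row.** Counted rate p = s·a + (1−s)·b. With a = 30%, b = 8%, s = 1/3: 10.0 + 5.3 = 15.3%. Range at a = 30%: from 8.4% (b = 3%, s = 0.2) to 25.0% (b = 15%, s = 2/3).

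**Step 2: 30/45 µg against 60 µg at 9-17 years.** Shift = (difference in 9-11 share) × (a − b). With a − b = 22 points, each 10-point difference in share moves the contrast by 2.2 points. A hypothetical 50% against 25% would move it by 0.25 × 22 = 5.5 points. Over a = 20-40% and b = 5-10%, that becomes 0.25 × (20−10) = 2.5 to 0.25 × (40−5) = 8.75 points. No such imbalance is documented.

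**Step 3: pooled tables.** Pooled rate = (1−h)·a + h·p, where h is the 9-17 share of the pool.
- 30 or 45 µg: 0.75×30 + 0.25×15.3 = 26.3%.
- 60 µg: 0.818×30 + 0.182×15.3 = 27.3%. The difference is 1.0 point.
- In general the difference is (0.250 − 0.182)(a − p). It runs from 0.2 points (a = 20%, p = 16.7%) to 1.5 points (a = 30%, p = 8.4%).
- Protocol 12.1.1.2 allows optional pooling over both countries. Adding Group 8 at 60 µg gives h = 30/195 = 15.4% and an upper end of (0.250 − 0.154) × 21.6 = 2.1 points.
- QIV-HD against matched QIV-SD: h is equal on both sides, so the expected spurious difference is zero.

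**Step 4: chance age imbalance between randomised arms.** For 30 versus 10 children, the SD of the difference due to age mix is 22 × √[(1/3)(2/3)(1/30 + 1/10)] = 3.8 points; for 30 versus 30 it is 2.7. This is already inside the binomial variance, because s·a(1−a) + (1−s)·b(1−b) + s(1−s)(a−b)² = p(1−p): 0.0700 + 0.0491 + 0.0108 = 0.1298. The age part is 0.0108/0.1298, about 8%. The total SD for 30 versus 10 is √[0.1298 × (1/30 + 1/10)], about 13 points.

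**Step 5: fever.** A reading of 39.5 °C is Grade 2 under 36 months and Grade 3 from 3 years. That age cut coincides with an age-group boundary, so only pooled grades mix scales. Children under 36 months make up 30/120 = 25% of the 30 and 45 µg pools and 60/165 = 36% of the 60 µg pool. The documents give no fever rates, so the shift cannot be sized.

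**The case against.** The case against acting is substantial, and most of it stands.

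- **Interpretability.** A reader might infer that the 9-17 and pooled rates cannot be interpreted at all. The documents do not support that. Within Group 12 and within Group 13, both vaccines are randomised together and graded by one rule. For pooled tables SAP 5.1.1.2 raises Simpson's paradox itself, and its restricted QIV-SD groups match the planned 9-17 shares exactly.
- **Added noise.** One might treat the 3.8-point SD in Step 4 as extra uncertainty. It is a component of ordinary sampling variance, and the reported intervals already cover it in expectation.
- **A built-in advantage for 60 µg at 9-17 years.** Sequential enrolment makes an age shift possible, but nothing suggests that younger children enrol first. Group 13 also has 30 QIV-SD controls of its own, who would share the shift.
- **Breadth.** Pain, which Protocol 1.3.2 names (with tenderness) as the most frequent side effect, has no size threshold.
- **Weight in the dosage choice.** The documents assign reactogenicity no weight in choosing the Phase III dosage. The Stage 4 dosage follows the early safety review, which excludes ages 9 to 17 and whose explicit triggers are related SAEs and Grade 3 fever.
- **Disclosure.** The scales are prespecified, consistent across both documents and openly noted. SAP section 7 defers outputs to a full set of tables that is not included, so a split or footnote there cannot be ruled out.

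What survives is the absolute rate. Randomisation does not make a blend of two definitions into a rate under either one, and neither document's text provides a split or a common threshold.

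**Conclusion.** The concern holds in limited form. For erythema, swelling, induration and bruising, and any composite containing them, the 9-to-17-year occurrence and Grade 3 rates describe neither definition and move with an age mix that is not a randomisation stratum. Under the illustrative assumptions a 30% any-size rate and an 8% rate at 25 mm or more appear as about 15%; over the wider grid, 30% is counted as 8% to 25%. These sizes rest on assumed rates and assumed age shares.

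Comparisons are much less affected. Randomised and matched high-dose versus standard-dose contrasts are unbiased in expectation. The expected pooled shift between dosages is about 1.5 points or less (about 2.1 if Group 8 is pooled in at 60 µg). The 30/45 µg versus 60 µg contrast at 9-17 years is exposed only if the age mix of Groups 12 and 13 differs, which is not documented. For fever the mixing is confined to Grades 2 and 3 in pooled tables. This is a cheap improvement in reporting for a descriptive, unpowered study.

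**What to change.** In SAP 4.4.1.1 and 5.1.1.2:

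1. Keep the protocol's age-specific grades in all per-age-group tables, but show the four measured reactions separately for 9-11 and 12-17 years.
2. In the 9-to-17 and age-pooled tables, add rows that apply one rule at all ages: above 0 mm, at least 25 mm, at least 50 mm and above 100 mm. Count reactions too large to measure, which the SAP already sets to Grade 3, in the largest category.
3. In the age-pooled tables, add common temperature rows: at least 38.0 °C, at least 39.0 °C and above 39.5 °C, using the Fahrenheit equivalents in the protocol tables (at least 100.4 °F, at least 102.1 °F and above 103.1 °F) for readings taken in that unit.
4. Footnote the two scales wherever ages are combined.

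This changes no data collection, intensity scale or safety-review criterion. Millimetres and temperatures are recorded and graded at analysis, so the cost is programming and a few extra table rows.

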4.4.1.1.2 Maximum Intensity

Maximum intensity is derived from the daily intensities computed as described in [Section 4.4.1.1.1](#) and is calculated as the maximum of the daily intensities over the period considered.

4.4.1.1.3 Occurrence

Occurrence is derived from the maximum intensity on the period considered:

- None: No occurrence
- Grade 1, Grade 2, or Grade 3: Occurrence
- Missing: Missing occurrence

Subjects with at least one non-missing occurrence for a specific endpoint will be included in the analysis. Conversely, those without a non-missing occurrence will not be included in the analysis of the endpoint.

4.4.1.1.4 Time of Onset

Time of onset is derived from the daily intensities computed as described in [Section 4.4.1.1.1](#). It corresponds to the first day with intensity of Grade 1, Grade 2, or Grade 3.

Note: If a reaction is not continuous (ie, reaction occurs over two separate periods of time intervened by at least one daily intensity Missing or None) then the time of onset is the first day of the first occurrence.

Table 4.1: Categories for time of onset

Injection Site Reactions (D0-D7)	Systemic Reactions (D0-D7)
D0-D3	D0-D3
D4-D7	D4-D7

4.4.1.1.5 Number of Days of Occurrence

Number of days of occurrence over the period considered is derived from the daily intensities computed as described in [Section 4.4.1.1.1](#). It corresponds to the number of days with daily intensities of Grade 1, Grade 2, or Grade 3. Number of days of occurrence during the solicited period with a specified intensity may also be derived.

Table 4.2: Categories for number of days of occurrence during the solicited period

Injection Site Reactions (D0-D7)	Systemic Reactions (D0-D7)
1-3 days	1-3 days
4-7 days	4-7 days
8 days	8 days

4.4.1.1.6 Overall Number of Days of Occurrence

If a reaction is ongoing at the end of the solicited period, then the overall number of days of occurrence is derived from the daily intensities and the stop date of the reaction after the end of the solicited period. The overall number of days of occurrence is:

- $(\text{stop date} - \text{vaccination date}) + (\text{number of days of occurrence within the solicited period}) - \text{length of the solicited period} + 1$.

If the stop date is missing or incomplete (containing missing data [MD]), the overall number of days of occurrence will be considered as Missing.

Table 4.3: Categories for overall number of days of occurrence

Injection Site Reactions	Systemic Reactions
1-3 days	1-3 days
4-7 days	4-7 days
≥ 8 days	≥ 8 days
Missing	Missing

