#### **9.1.3.2 Reactogenicity (Solicited Reactions From Day 0 to Day 7 After Each Vaccination)**

After each vaccination, subjects / parents / guardians will be provided with a diary card, a digital thermometer, and a flexible ruler, and will be instructed how to use them. The following items will be recorded by the subjects in the diary card on the day of vaccination and for the next 7 days (ie, D0 to D7) until resolution:

- Daily temperature, with the route by which it was taken
- Daily measurement or intensity grade of all other solicited injection site and systemic reactions
- Action taken for each event (eg, medication)

The action(s) taken by the subject / parent / guardian to treat and/or manage any **solicited reactions** will be classified in the CRB using the following list (all applicable items should be checked):

- None
- Medication
- Health care provider contact
- Hospitalized
- Discontinuation of study vaccination

[Table 9.1](#), [Table 9.2](#), [Table 9.3](#), [Table 9.4](#), and [Table 9.5](#) present, respectively, the injection site reactions and systemic reactions that are prelisted in the diary cards and CRB, together with the intensity scales.

**Table 9.1: Solicited injection site reactions for infants and toddlers aged < 36 months: terminology, definitions, and intensity scales**

CRB term (MedDRA LLT)	Injection site tenderness	Injection site erythema	Injection site swelling	Injection site induration	Injection site bruising
MedDRA PT	Injection site pain	Injection site erythema	Injection site swelling	Injection site induration	Injection site bruising
Diary card term	Tenderness	Redness	Swelling	Hardening	Bruising

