4.4.1.1.7 Ongoing

Ongoing is derived from the last daily intensity of the solicited period computed as described in [Section 4.4.1.1.1](#) and the maximum intensity on the ongoing period. The investigator's ongoing flag is not used because the measurement would determine the ongoing status of the reaction.

Note: a reaction could be derived as not ongoing for the analysis despite being considered as ongoing by the investigator (eg, when the maximum measurement after D7 is > 0 mm but < 25 mm for 12 to 17 years of age). If the last daily intensity of the solicited period is at least Grade 1 and maximum intensity on the ongoing period is also at least Grade 1, then the reaction is considered ongoing. In any other cases the reaction will not be considered as ongoing.

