5.3.1.5 Start Date and Stop Date

Missing or partially missing start dates for unsolicited AEs will remain missing and will not be imputed. If either the start or stop date is missing or partially missing, the time of onset will be considered to be missing. Nevertheless unsolicited AEs with missing time of onset will be included in analyses according to the visit collected.

Missing or partially missing stop dates for AEs (solicited reactions and unsolicited AEs) will remain missing and will not be imputed.

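### A missing or partial stop date sends an ongoing solicited reaction to 'Missing' overall duration even when the recorded data already prove 8 days or more (minor)

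*SAP*

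**What the plan says.** SAP 4.4.1.1.6 applies to reactions that are ongoing at the end of the solicited period. It adds the days from vaccination to the stop date to the "number of days of occurrence within the solicited period", subtracts the length of the solicited period and adds 1. Its rule for incomplete data is: "If the stop date is missing or incomplete (containing missing data [MD]), the overall number of days of occurrence will be considered as Missing". The results go into four rows, set out in Table 4.3: 1-3 days, 4-7 days, ≥ 8 days and Missing.

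Three other provisions matter:

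- SAP 4.4.1.1.7 derives ongoing status from intensities, not from a stop date. The last daily intensity of the solicited period must be at least Grade 1, and if the "maximum intensity on the ongoing period is also at least Grade 1, then the reaction is considered ongoing". A reaction can therefore be ongoing with no stop date on file.
- SAP 4.4.1.1.5 counts the days within the solicited period from the daily records alone: "It corresponds to the number of days with daily intensities of Grade 1, Grade 2, or Grade 3".
- SAP 5.3.1.5 offers no rescue: "Missing or partially missing stop dates for AEs (solicited reactions and unsolicited AEs) will remain missing and will not be imputed".

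**The concern.** The rule never consults the daily records when the stop date is absent, although those records can be enough to place the reaction in an open-ended category. Only reactions that outlast D7 can be affected, so the information lost concerns persistent reactions. It also produces an odd ordering. On the natural reading, a reaction present on all of D0 to D7 that ends on D7 counts as 8 days and falls in '≥ 8 days'. A longer reaction, present on all eight days and continuing with no recorded stop date, is 'Missing'.

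At stake is the accuracy of one row of a descriptive safety table in a study meant to inform the choice among 30, 45 and 60 µg. Most arms have 30 or 10 children, so a single misplaced case is visible in the percentages.

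**Working it through.** The plan states no figure for this point, so there is none to reproduce. The check applies the SAP's own formula to the earliest stop date that the derived status allows.

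**Inputs**

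- Length of the solicited period: 8 days. Protocol 9.1.3.2 has items recorded "on the day of vaccination and for the next 7 days (ie, D0 to D7) until resolution", and the top row of SAP Table 4.2 is 8 days.
- k: number of days in D0 to D7 at Grade 1 or above (SAP 4.4.1.1.5).
- Earliest stop: D8. SAP 4.4.1.1.7 requires at least Grade 1 on D7 and at least Grade 1 after D7.
- Formula (SAP 4.4.1.1.6): overall days = (stop date − vaccination date) + k − 8 + 1.

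**The formula behaves correctly when the stop date is known.** A continuous reaction from D0 to D10 gives 10 + 8 − 8 + 1 = 11 days. A reaction from D7 to D9 gives 9 + 1 − 8 + 1 = 3 days. Both are right.

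**Stop date wholly missing.** With stop = D8, the minimum is 8 + k − 8 + 1 = k + 1.

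| k | Minimum overall days | '≥ 8 days' proven? | SAP result |
|---|---|---|---|
| 1 to 6 | 2 to 7 | no | Missing |
| 7 | 8 | yes | Missing |
| 8 | 9 | yes | Missing |

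The bound does not depend on the formula: k recorded days plus at least one day after D7 is at least k + 1. If the period length were taken as 7 instead of 8, the formula would give k + 2 and the threshold would move to k = 6, but D0 to D7 and Table 4.2 support 8.

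**Stop date partial.** Take vaccination on 10 October and a stop date with the day missing in November. The earliest stop is 1 November, 22 days after vaccination, so the minimum is 22 + k − 8 + 1 = 15 + k, that is 16 days (k = 1) to 23 days (k = 8). The category is certain for every k, and the rule still gives 'Missing'. If the recorded month is October, the month adds nothing and the D8 bound of k + 1 applies.

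**Illustration of size.** The counts are assumptions. The full arm is the denominator, every long reaction is taken as provable, and intervals are Clopper-Pearson 95%.

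| Arm size | Provable '≥ 8 days' | Of these, no usable stop date | Under the SAP rule | Using the minimum |
|---|---|---|---|---|
| 10 | 1 | 1 | 0.0% (0.0-30.8) | 10.0% (0.3-44.5) |
| 30 | 3 | 1 | 6.7% (0.8-22.1) | 10.0% (2.1-26.5) |
| 45 | 3 | 1 | 4.4% (0.5-15.1) | 6.7% (1.4-18.3) |

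Each lost case costs 1/10 = 10 points, 1/30 = 3.3 points or 1/45 = 2.2 points.

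**The case against.** The case for leaving the rule alone has several parts, and much of it stands.

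- **Missing stop dates should be few.** Protocol 9.1.1 treats solicited reactions as related. Protocol 5.1.4 requires related events to be followed until they resolve, stabilise or become chronic. A footnote in Protocol 9.1.3.3, in the section on unsolicited events, has the stop dates of related events actively sought. This limits the number of cases but does not make the rule correct for those that remain.
- **The loss is disclosed.** Table 4.3 prints a 'Missing' row, and adding it to '≥ 8 days' gives an upper bound. That stands, but the row mixes proven cases with reactions of k ≤ 6 whose category is open, so a reader cannot separate them.
- **Table 4.2 needs no stop date.** A k = 8 reaction still appears there as 8 days. A k = 7 ongoing reaction, however, appears there as 4-7 days and in Table 4.3 as Missing, so its proven duration appears in neither.
- **The listed endpoint is narrower.** Protocol 9.1.2 asks for the number of days of occurrence of reactions up to 7 days after vaccination, so Table 4.3 is a further display. Occurrence, intensity and onset are unaffected. This argues for low severity.
- **The rule follows the plan's no-imputation convention.** It does, but assigning a category that the data already prove does not require imputing a date.

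A reader might infer that a substantial share of long reactions is hidden, or that dosage selection is biased. The documents support neither. They give no rate of missing stop dates, the same rule applies to every arm, no hypothesis is tested, and the specific occurrences examined in the early safety reviews are a related SAE and Grade 3 fever in more than 10% of subjects, not duration. Nor does every ongoing reaction without a stop date belong in '≥ 8 days': with k ≤ 6 and no informative partial date, 'Missing' is the honest result.

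**Conclusion.** The point holds in a limited form and is minor. The rule misclassifies reactions whose category is already determined: those derived as ongoing with k = 7 or 8, and those whose partial stop date sets a minimum of at least 8 days. For these the error runs one way, out of '≥ 8 days' and into 'Missing'. The conclusion rests on an 8-day solicited period and on the SAP's own definition of ongoing. The number of children affected is unknown and probably small, and the percentages in the illustration depend wholly on assumed counts. The consequence is confined to the overall-duration display.

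**What to change.** Replace the sentence in SAP 4.4.1.1.6 with:

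> If the stop date is missing or incomplete, compute the minimum overall number of days from the formula using the later of D8 and the first day of any recorded month or year of the stop date. If this minimum is ≥ 8, classify as '≥ 8 days'; otherwise classify as 'Missing'.

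The phrase 'the later of' is needed. With vaccination on 10 October and a stop date known only as October, starting from 1 October would give −9 + 8 − 8 + 1 = −8 for k = 8 and would wrongly leave the case as 'Missing'.

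Add to SAP 5.3.1.5 that the stop date itself stays missing and is not imputed, and that only the duration category is assigned by this lower bound. That keeps the two sections consistent.

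The cost is two short SAP edits and a small programming change, with no new data. The '≥ 8 days' percentages may rise slightly.
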